PLANNED INTERIM ANALYSES	An interim analysis is planned after approximately 30% of the patients have been enrolled and completed follow-up to assess safety and provide estimates of within and between patient variability in the recovery time of muscle relaxants. The interim analysis for safety will be conducted by the study team. Serious adverse events will be monitored by the investigators on an ongoing basis throughout the study.
STATISTICS Primary Analysis Plan	This is a two-period, two-treatment, 2x2 cross-over study. Although it is highly likely that the washout period is adequate for eliminating the first order carry-over effects since all repeated procedures are scheduled at least 48 hours apart, which exceeds the duration for all the involved medications, we will exam the period and carryover effects using a term for time period and an interaction term between the treatment group and time period. Intent-to treat analyses will be used for primary and secondary outcomes. For the primary outcome, the comparison of recovery time of T1 to 90% baseline, a continuous variable, between the groups of rocuronium /sugammadex and the

	succinylcholine /saline placebo, will be analyzed using the two sample t test.
Rationale for Number of Subjects	
Based on the study by Lee, et al,⁸ comparing high dosage of rocuronium 1.2 mg/kg in combination with high dosage reversal of sugammadex 16mg/kg with succinylcholine 1mg/kg, the recovery time T1 to 90% in succinylcholine was 10.9 ± 2.4 minutes. The reported T1 to 90% 4mg/kg sugammadex reversed recovery counted from time of rocuronium 0.6 mg/kg (the same proposed dosage as in our study) administration ranged from 6 to 9.3 minutes.^{5, 10} With our estimation of two-tailed $\alpha=0.05$, $\beta=0.2$, the reported minimum mean difference of 1.6 (10.9 minus 9.3) minutes, SD of succinylcholine of 2.4 minutes, the calculated sample size for a cross-over trial would be 35.
 
At UCSF, there are usually 60 ECT patients each year. With a conservative estimate of 75% consent rate, we will have at least 45 patients to participate in the study. Even conservatively allowing a 20% drop-off rate, we feel that our enrollment up to 50 will provide sufficient power for the study.

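### Is the crossover sample size of 35 a parallel-group figure that leaves the trial short of 80% power?

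*Combined protocol and SAP*

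**What the plan says.** The synopsis sets the number of subjects at 50. Under Statistics, the Primary Analysis Plan describes the design: "This is a two-period, two-treatment, 2x2 cross-over study". It says the primary outcome, time to recovery of T1 to 90% of baseline, "will be analyzed using the two sample t test".

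Rationale for Number of Subjects supplies the inputs. From a published comparison, "the recovery time T1 to 90% in succinylcholine was 10.9 ± 2.4 minutes". For rocuronium reversed by sugammadex at the study doses, the reported times run from 6 to 9.3 minutes. The calculation uses "the reported minimum mean difference of 1.6 (10.9 minus 9.3) minutes" and the "SD of succinylcholine of 2.4 minutes", with two-sided alpha 0.05 and beta 0.2. It concludes that "the calculated sample size for a cross-over trial would be 35". No formula, SD of paired differences or within-patient correlation is given.

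The accrual argument follows: about 60 ECT patients a year, 75% consenting, hence at least 45. It closes: "Even conservatively allowing a 20% drop-off rate", enrolment of up to 50 is judged sufficient. Planned Interim Analyses adds that within- and between-patient variability will be estimated after about 30% of patients.

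**The concern.** A crossover is sized on the variability of within-patient differences. The plan uses an SD observed across patients on one treatment and says nothing about correlation between periods. The result matches the textbook per-arm size for two independent groups, so it is natural to suspect that a parallel-group formula was run and relabelled.

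Three further signs point the same way. The formula gives 35.3, which should round up. A t-based crossover calculation on the same inputs asks for 38. If 2.4 were the SD of differences, 20 would be enough, so 35 seems to fit neither reading. The accrual check appears to pass only because it is set against 35: 45 less 20% is 36, which clears 35 but not 38.

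If this were right, the stated 80% power would not belong to the design, and the trial could miss a true difference of 1.6 minutes more often than the plan says.

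**Working it through.** **Inputs**, all from Rationale for Number of Subjects: difference δ = 10.9 − 9.3 = 1.6 minutes; SD σ = 2.4 minutes; two-sided alpha 0.05; power 80%; drop-off 20%; enrolment up to 50. **Assumptions**, because the documents give no figure: the SD is the same under both treatments, and the within-patient correlation ρ is varied.

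**1. The plan's figure.** With (1.960 + 0.842)² = 7.849, the per-arm size for two independent groups is

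2 × (σ/δ)² × 7.849 = 2 × (2.4/1.6)² × 7.849 = 2 × 2.25 × 7.849 = 35.32.

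So 35 reproduces to rounding (36 if rounded up).

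**2. The crossover figure.** The within-patient difference has variance 2σ²(1 − ρ). The total number of patients is

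n = 2σ²(1 − ρ) × 7.849 / δ² = 35.32 × (1 − ρ).

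At ρ = 0 this is 35.32 again. The per-arm size of a parallel trial and the total size of a zero-correlation crossover are the same number, because each crossover patient supplies one observation per treatment: 35 patients give 35 on each. The figure therefore cannot tell the two calculations apart, and as a crossover size it is correct for ρ = 0.

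**3. Power with 35 completers at ρ = 0.** The SD of differences is 2.4 × √2 = 3.394, the standard error is 3.394/√35 = 0.574, and δ/SE = 2.79.

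- Normal approximation: 79.6%
- Two-sample t test, as named in the plan: 78.5%
- Crossover t with 33 degrees of freedom: 77.2%

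**4. Effect of correlation** (crossover t, n − 2 degrees of freedom):

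| ρ | completers for 80% power | power with 35 | power with 40 |
|---|---|---|---|
| 0 | 38 | 77.2% | 82.8% |
| 0.1 | 34 | 81.4% | 86.5% |
| 0.2 | 31 | 85.7% | 90.1% |
| 0.3 | 27 | 89.9% | 93.5% |
| 0.5 | 20 | 96.9% | 98.4% |

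Power with 35 reaches 80% at ρ of about 0.07. Reading 2.4 as the SD of differences is the ρ = 0.5 row, since 2.4 × √(2 × 0.5) = 2.4. On that reading 35 is generous.

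**5. Completers the plan provides for.** Fifty enrolled less 20% leaves 50 × 0.8 = 40. At ρ = 0, that gives 82.8% by crossover t and 83.8% by the two-sample t test. The strict t-based requirement of 38 completers needs 38/0.8 = 47.5, so 48 enrolled, which is within 50.

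The less favourable count is 60 × 0.75 = 45 and 45 × 0.8 = 36. At ρ = 0, 36 completers give 78.5% by crossover t, and they pass 80% at ρ of about 0.04.

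**6. Choice of difference.** The 1.6 minutes is the smallest the cited times allow. The other end of the range gives 10.9 − 6 = 4.9 minutes.

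**The case for a change.** The strongest case is that, on the stated inputs with no correlation, 35 falls short of 80% by every calculation: 79.6%, 78.5% and 77.2%, which need 36, 37 and 38 patients. The accrual paragraph projects 45 consenting patients a year, which leaves 36 completers rather than 40. The parameter that drives a crossover's size is not stated, so a reader cannot tell whether 35 is tight or generous.

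The arithmetic stands, but it does not carry the conclusion. The shortfall is at most about 3 points. It comes from rounding 35.3 down and from using the normal in place of the t distribution, not from using a one-treatment SD. Using that SD without credit for correlation is the cautious choice for any positive ρ. The 45 is worded as a minimum, while the synopsis and the rationale both set the study at up to 50. That 35 is odd does not matter, because it is a calculated requirement and not the number to be randomised.

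What remains is that the plan does not say it treats ρ as zero. That is a gap in documentation. The interim look is designed to estimate the missing variability. Whether a two-sample t test suits a crossover is a separate question about the analysis; the power figures for both tests lead to the same answer here.

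**Conclusion.** The concern does not hold. The 35 is the right crossover size, to rounding, for zero within-patient correlation. The enrolment actually planned gives 82.8% power in that case and more with any positive correlation. Restating the calculation by t distribution would raise the requirement to 38 completers, or 48 enrolled, and leave the planned 50 unchanged.

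This rests on three conditions: equal SDs under the two treatments, enrolment close to 50 with no more than 20% lost, and no negative correlation between a patient's two recovery times. At ρ = −0.25, power with 35 would fall to 67.8% by crossover t. A larger SD under rocuronium and sugammadex would also lower power. The documents give no sign of either.
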